6.8.4 Retention of Records

Records and documents pertaining to the conduct of this study, including patient's data, Informed Consent Forms and Trial Master File, must be retained by the physician for at least 15 years after completion or discontinuation of the study, or for the length of time required by relevant national (or foreign countries) or local health authorities, whichever is longer. The

Sponsor will inform the Investigator as to when the documents no longer need to be retained. After that period of time, the documents may be destroyed, subject to local regulations.

No records may be disposed of without the written approval of the Sponsor. Written notification should be provided to the Sponsor prior to transferring any records to another party or moving them to another location.

All supporting functional parties will comply with the Sponsor procedures regarding archiving and record management.

6.8.5 Administrative Structure

For this study, a Steering Committee will be organized. The role of the Study Steering Committee is to provide overall supervision of the study and ensure that it is being conducted in accordance with the study protocol, principles of Good Pharmacoepidemiological Practice (GPP), EU Guideline on Good Pharmacovigilance Practices (GVP) and the relevant regulations. The Study Steering Committee should agree the study protocol and any protocol amendments and provide advice to the investigators on all aspects of the study.

6.9 LIMITATIONS OF THE RESEARCH METHOD

Sites participating in this study will not cover the entire Italian territory and, therefore, caution should be used in the generalisation of data collected in this study to the activity status, bleed, HRQoL and health status in patients with Haemophilia A without inhibitors receiving standard of care treatment in routine clinical practice in Italy.

Furthermore, data collected in this study are encompassing an observational period of 12 months (up to 18 months for patients who will start treatment any newly approved drugs) and, therefore, information of data retrieved in this study is to be considered as limited to the study period and cannot be generalised as data of health status in patients with Haemophilia A in the forthcoming years.

7. PROTECTION OF HUMAN SUBJECTS

7.1 COMPLIANCE WITH LAWS AND REGULATIONS

This study will be conducted in full conformance with the Guidelines for GPP published by the International Society of Pharmacoepidemiology (ISPE) and the laws and regulations of the country (Italy) in which the research is conducted.

7.2 INFORMED CONSENT

The Sponsor's sample Informed Consent Form (and ancillary sample Informed Consent Forms such as a specific patient and parent/caregiver's Informed Consent Form for patients aged 12-17 years) will be provided to each site. The Informed Consent Form will be provided in the local language. The Sponsor must review and approve any proposed deviations from the Sponsor 's sample Informed Consent Forms or any alternate Consent Forms proposed by the site (collectively, the "Consent Forms") before EC submission. The final Consent Forms approved by the EC must be provided to the Sponsor for health authority submission purposes according to local requirements.

The Consent Forms must be signed and dated by the patient (and by parent/caregiver for patient aged 12-18 years) before performing any study-specific evaluation. The case history or clinical records for each patient shall document the informed consent process and that written informed consent was obtained prior to first documentation of this patient's data in the eCRF.

By signing the form, the patient (and parent/caregiver for patient aged 12-17 years) confirms that he/she has been informed about the study and agrees to pseudonymous data collection, pooling of data with similar scientific data (if applicable), and the possibility of monitoring activities. It is the responsibility of the physician to obtain written informed consent from each patient (and from parent/caregiver for patient aged 12-17 years) participating in the study, after adequate explanation of the aims, methods, anticipated benefits, and potential hazards of the study. The physician must also explain that the patient (and parent/caregiver for patient aged 12-17 years) is completely free to refuse to enter the study or to withdraw from it at any time, for any reason and without losing the benefit of any medical care to which the patient is entitled or is presently receiving.

A copy of each signed Consent Form must be provided to the patient (and to parent/caregiver for patient aged 12-17 years). All signed and dated Consent Forms must remain in each patient's study file or in the site file and must be available for verification by Site Operations Representative at any time.

7.3 ETHICS COMMITTEE

This protocol, the Informed Consent Forms, any information to be given to the patient, and relevant supporting information must be submitted to the EC and reviewed and approved by the EC before the study is initiated. In addition, any patient recruitment materials must be approved by the EC.

7.4 CONFIDENTIALITY

The Sponsor maintains confidentiality standards by coding each patient enrolled in the study through assignment of a unique patient identification number. This means that patient names are not included in datasets that are transmitted to any Sponsor location.

Patient medical information obtained by this study is confidential and may be disclosed to third parties only as permitted by the Informed Consent Form (or separate authorization for use and disclosure of personal health information) signed by the patient, unless permitted or required by law.

Medical information may be given to a patient's personal physician or other appropriate medical personnel responsible for the patient's welfare, for treatment purposes.

Data generated by this study must be available for inspection upon request by representatives of national (or foreign countries) and local health authorities, Sponsor monitors, representatives, and collaborators, and the EC for each study site, as appropriate.

8. MANAGEMENT OF ADVERSE EVENTS

Although adverse event information is not being actively solicited via this protocol, physician/consumers are reminded to report any adverse reactions (for which they suspect a causal role of a product) or special situations either to the marketing authorization holder of the suspected product, via the Roche Adverse Event and Special Situation Reporting Form (SRD-0120176) (for Roche products), or to the concerned competent authorities via the national spontaneous reporting system.

8.1 Reporting Requirements for Adverse Events originating from Patient Reported Outcomes

Although physician/study personnel are not expected to review the PRO data for potential adverse events, if physician/study personnel become aware of a potential adverse event during the review of the PRO questionnaire data, he/she will determine whether the criteria for an adverse event have been met and, if so, these must be reported using the Roche Adverse Event and Special Situation Reporting Form (SRD-0120176) (for Roche medicinal products), or to the concerned competent authorities via the national spontaneous reporting system.

9. PUBLICATION OF DATA AND PROTECTION OF TRADE SECRETS

Regardless of the outcome of a study, the Sponsor is dedicated to openly providing information on the study to healthcare professionals and to the public, both at scientific congresses and in peer-reviewed journals. The Sponsor will comply with all requirements for publication of study results.

The results of this study may be published or presented at scientific meetings. If this is foreseen, the physician must agree to submit all manuscripts or abstracts to the Sponsor prior to submission for publication or presentation. This allows the Sponsor to protect proprietary information and to provide comments based on information from other studies that may not yet be available to the physician.

In accordance with standard editorial and ethical practice, the Sponsor will generally support publication of multicentre studies only in their entirety and not as individual centre data. In this case, a coordinating physician will be designated by mutual agreement.

Authorship will be determined by mutual agreement and in line with International Committee of Medical Journal Editors' authorship requirements. Any formal publication of the study in which contribution of Sponsor personnel exceeded that of conventional monitoring will be considered as a joint publication by the physician and the appropriate Sponsor personnel.

Any inventions and resulting patents, improvements, and/or know-how originating from the use of data from this study will become and remain the exclusive and unburdened property of the Sponsor, except where agreed otherwise.

Appendix 1 List of Stand-Alone Documents Not Included in the Protocol

Not applicable

Appendix 2 Data Collection Overview (as per Standard of Care)

	Baseline	Observational period Study Completion/ Early Termination Visit		Patients starting any newly ¹ approved drugs between month 6 and month 12 ²				
Visit	1	2	3	4	5			
Time (months)*	0	3	6	9	12	Start of therapy	3 post- start	6 post- start
Informed consent ³	х							
Demographic data	х							
History of physical activity	х							
Medical history and history of Haemophilia (including history of anaphylaxis or known thrombophilia)	х							
Number of bleeds, number of school/work days missed and number of days hospitalized during 24 weeks prior baseline	x							
Inclusion/exclusion criteria	х							
Treatment for Haemophilia (including start of treatment with newly approved drugs)	Х	х	х	х	Х	х	х	х
Prior (in the 24 weeks before baseline) and Concomitant medications, including coagulation products	х	х	х	Х	Х	х	х	х

	Baseline	Obse	rvational	period	Study Completion/ Early Termination Visit ¹		nts starting a d drugs betw and month	een month 6
Visit	1	2	3	4	5			
Time (months)*	0	3	6	9	12	Start of therapy	3 post- start	6 post- start
Physical examination ⁴	x	х	х	х	Х		х	x
Vital signs (including height (at baseline only), weight and BMI (at baseline and every 3 months)	х	х	х	х	Х		х	х
Downloading of ePRO application and training in its use ⁵	х							
Dispensing of fitness tracker and downloading of related application								
Physical activity ⁶	х	← Daily →		← Daily →				
Bleeding and treatments for bleeding (via ePRO) ⁷	х	← When bleeding occurs →		← When bleeding occurs →		occurs →		
VAS for pain (via ePRO)8	х	← Monthly →			← Monthly	→		
EQ-5D-5L (via ePRO) ⁹	х	х	х	х	х		х	х
Joint health status (HJHS) 12	х		х		х			х

	Baseline	Obse	ervational	period	Study Completion/ Early Termination Visit ¹	approved of	s starting any drugs betwee and month 12	n month 6
Visit	1	2	3	4	5			
Time (months)*	0	3	6	9	12	Start of therapy	3 post- start	6 post- start
Days away from school (patients) or work (patients and/or caregivers), age of possible early retirement (caregiver), (via ePRO) ¹⁰		← Monthly →		← Monthly →		→		
Days of hospitalization related to haemophilia (patients) (via ePRO)				← Mor	nthly →		← Monthly -	→
Evaluation of start a newly approved drug therapy		X	X	X	х			
Any relevant surgeries or procedures		X	X	X	Х	Х	Х	Х

^{*} Visits at the clinic will be performed approximately every three months, but some degree of flexibility (e.g. ± 1 month) will be considered according to Investigator's judgment and local clinical practice.

¹ In case of early study discontinuation (for any reason), procedures will be those scheduled for Visit 5 (study completion visit)

- ² Patients who will start treatment with any newly approved drugs (see section 2 exploratory objectives), between Month 6 and Month 12 will complete a 6-month observational period after the switch, and therefore the entire observational period in these patients may be prolonged up to 18 months. They will also perform the Study Completion/ Early Termination Visit as their last visit.
- ³ The Consent Forms must be signed and dated by the patient (if aged ≥18 years) and by parent/caregiver (for patient aged 12-17 years) before start of documentation of his/her data in the eCRF.
- ⁴ A complete physical examination will be performed at baseline (if planned as per standard routine of care) and at least targeted physical examinations will be performed at all follow-up visits
- The ePRO application downloaded on the patient's own device) will be used by patients to record data on bleeds, bleeds treatment, HRQoL, number of days away from school (patients) or work (patients and/or caregivers), age of possible early retirement (caregiver), number of hospitalization days (patients) and VAS for pain. In patients who will start treatment with any other newly approved drugs (see section 2 exploratory objectives), measurements of the parameters listed above through ePRO application will be also performed at the time of start of treatment with any newly approved drugs, and for at least 6 months following the start of treatment.
- ⁶ Physical activities will be measured by wearing a study device continuously during study participation. At baseline, information about physical activity in the previous 24 weeks will be collected if available.
- Bleeding and treatments for bleeds will be reported in a continuous manner, during study participation. Patients will be prompted electronically on a monthly basis to report any bleeds. In case of bleeds, patients will report bleed information, including site of bleed, type of bleed, time of each individual bleed (date, start time and end time), symptoms of bleed, treatment for bleed and health status information. The following information on treatments for bleeds will be reported: agent, start time, dose, route of administration, and number of infusions needed to treat the bleed. At baseline, information about any bleedings which occurred in the previous 24 weeks will be collected.
- ⁸ VAS for pain will be evaluated at baseline, monthly and at the end of study.
- ⁹ EQ-5D-5L for pain will be evaluated at baseline, every 3 months and at the end of study
- ¹⁰ Evaluated at baseline, monthly and at the end of the study
- ¹¹ HJHS will be evaluated at baseline, at 6 months and at the end of the study. HJHS will be also performed at the time of start of treatment with any newly approved drugs, and at 6 months following the start of treatment drugs.

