- Bleeds related to procedure/surgery: such as hematomas resulting from any surgeries or invasive procedures (e.g., tooth extractions, venepuncture, or subcutaneous drug administrations) or invasive diagnostic procedures (e.g., lumbar puncture, arterial blood gas determination, or any endoscopy with biopsy, etc.) would not be counted as bleeds. Bleeds related to procedure/surgery are not associated with any trauma except procedure/surgery-induced trauma.

Patients and parents/caregivers (for patients aged 12-17 years) will record bleeds in the ePRO application whenever a bleed occurs, and monthly to confirm that all bleeds have been recorded. Patients will be requested to answer the following question: 'Have you experienced any bleed in the last month?' In case of a positive answer, for each bleeding episode patients and caregivers will provide information on the above topics as well as on the medication used to treat the bleed.

Haemophilia medications that were taken will also be collected through the ePRO application.

Haemophilia Joint Health Score

The HJHS (Appendix 4) is an instrument developed to measure joint health status and to identify early signs of joint disease in children. This tool assesses joints most commonly affected by bleeding (knees, ankles, and elbows) (*Feldman et al. 2008*). Each of the 6 joints is assessed across 8 domains (Swelling, Duration of Swelling, Atrophy, Crepitus, Flexion Loss, Extension Loss, Pain, and Strength), and a Total Score is calculated as the sum of all joint domain scores. The instrument also includes a measure of Global Gait, which encompasses assessments of 4 skills: walking, stairs, running, and hopping on 1 leg.

The HJHS will be completed at baseline, at six months and at the end of the study.

HRQoL

The patient (or the patient's legally authorized representative) will report via the ePRO application, HRQoL using the EQ-5D-5L questionnaire in both adults and adolescents (Appendix 5).

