**Treatment regimen for bleeding**

The following information collected in the eCRF will be shown to describe the treatment for bleeding:

- number and proportion of treated bleedings
- number and proportion of bleeds treated with each type of treatment for bleeding (haemostatic treatment, treatment for pain)
- duration of treatment for bleed (hours)
- number and proportion of bleeds treated with each route of administration

- number and proportion of bleeds which needed to receive a transfusion
- number and proportion of bleeds which needed to administer an additional hemostatic therapy
- number and proportion of bleeds which with adherence to the treatment regimen in the week preceding the bleeding.

A listing with complete information on each bleed and its treatment will be also provided.

Treatment regimen for bleed will also be analyzed by the intensity of physical activity done in the 2 days preceding the day of bleeding. Intensity of physical activity will be defined considering the MVPA done in the 2 days before the bleeding. MVPA minutes will be summarized as median of the values recorded in the 2 valid days before the bleeding. A median greater than 0 minutes will mean an intense physical activity (in case of only one valid day, that value will be used to summarize the physical activity preceding the bleeding).

Other subgroup analyzes: severity of the disease (see Section 4.4.5 for subgroup definition).

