### **Bleeding and daily physical activity.**

The relationship between bleedings and physical activity (daily and by type) will be done as described in Section 4.4.1 but considering only data collected by the fitness tracker in the two days preceding the day in which the bleeding occurs.

For the relationship with daily physical activity, only data in the valid days will be considered. For each bleeding, the data collected in the two valid days before the bleeding will be summarized by the median. In case only one valid day is available, those values will be used to summarize the activity done before that bleeding.

All the activities recorded in the two days before the bleeding will be used regardless they occur in a valid day.

**To observe patients, on primary and secondary objectives, for additional 6 months if new therapies become commercially available for patients with Haemophilia A without inhibitors against FVIII, during the course of the study and if patient will start such treatments during the observation period.**

All the analysis proposed in sections 4.4.1 and 4.4.2 (except for the subgroup analyses) will be repeated by considering the start of any newly approved drug for haemophilia A during the study. See Section 4.4.4 for more details on this subgroup analysis.

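### Bleeds first entered at the monthly prompt may carry a misremembered onset date, and the SAP's two-day pre-bleed activity window has no check for this

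*Protocol*

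**What the plan says.** Entry of bleeds is primarily event-driven. Protocol Appendix 2, footnote 7, states that "Bleeding and treatments for bleeds will be reported in a continuous manner, during study participation" and continues: "Patients will be prompted electronically on a monthly basis to report any bleeds". Protocol 6.4.1 (Bleeds) explains how the two fit together: patients and caregivers "will record bleeds in the ePRO application whenever a bleed occurs, and monthly to confirm that all bleeds have been recorded". The monthly question is "Have you experienced any bleed in the last month", and "In case of a positive answer, for each bleeding episode patients and caregivers will provide information on the above topics". Those topics include the date, start time and end time of the bleed.

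Two analyses in SAP 4.4.2 depend on the recorded bleed day:

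- *Bleeding and daily physical activity* repeats the Section 4.4.1 summaries "considering only data collected by the fitness tracker in the two days preceding the day in which the bleeding occurs".
- *Treatment regimen for bleeding* groups bleeds by prior intensity: "MVPA minutes will be summarized as median of the values recorded in the 2 valid days before the bleeding". A median above 0 minutes counts as intense activity.

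Neither analysis uses the date on which the bleed was entered. SAP 4.4.3 (Sensitivity Analyses) reads NA.

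**The concern.** The monthly question is a backstop, but it is also a working route of entry. A bleed not logged at the time can be entered there in full, with an onset day recalled after as long as a month. A two-day window leaves almost no room for error in that day.

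The direction of the error matters. A date recalled too early brings in ordinary days and dilutes any pre-bleed pattern. A date recalled too late brings in the onset day, and then later days, under the label of pre-bleed activity. If patients move less after a bleed, that pulls the summary downwards.

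The first analysis is the only one that the SAP assigns to the exploratory objective on activity and bleeding. In the second, a shifted window can move a bleed across the cut at 0 MVPA minutes.

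**Working it through.** The plan states no figure for entry delay, share of late entries or date error, so there is nothing to reproduce. What follows is window arithmetic (no assumption about recall) and then a range under stated assumptions.

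**Step 1. Window arithmetic.** Let e = recorded onset day minus true onset day, in whole days. The window covers days e−2 and e−1 relative to true onset; the correct days are −2 and −1. The share of correct days is max(0, 2−|e|)/2.

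| e | Days covered | Wrong days | On or after true onset |
|---|---|---|---|
| −2 or earlier | −4, −3 or earlier | 2 of 2 | 0 of 2 |
| −1 | −3, −2 | 1 of 2 | 0 of 2 |
| 0 | −2, −1 | 0 of 2 | 0 of 2 |
| +1 | −1, 0 | 1 of 2 | 1 of 2 |
| +2 or later | 0, +1 or later | 2 of 2 | 2 of 2 |

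A date one day late adds only the onset day. Days after onset enter from two days late.

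**Step 2. Late-entered bleeds only.** Assumption: e is a normal error with mean 0, rounded to whole days, with SD 0.5 to 5 days. Then

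wrong-day share = 0.5 × P(|e| = 1) + P(|e| ≥ 2).

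For SD 1: P(|e| = 1) = P(0.5 < |Z| < 1.5) = 0.4835 and P(|e| ≥ 2) = P(|Z| > 1.5) = 0.1336, so the share is 0.2417 + 0.1336 = 0.375. A simulation of 1,000,000 draws per SD gives the same value and the rest of the row. Because the assumed error is symmetric, half of the wrong days lie on or after onset.

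| Error SD (days) | 0.5 | 1 | 2 | 3 | 5 |
|---|---|---|---|---|---|
| Wrong days | 16% | 38% | 63% | 74% | 84% |
| On or after onset | 8% | 19% | 31% | 37% | 42% |

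**Step 3. All bleeds.** Assumptions: a share f of bleeds is first entered at the prompt, and bleeds entered when they occur have the correct date. The wrong-day share over all bleeds is f times the first row above.

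| f | SD 0.5 | SD 1 | SD 2 | SD 3 | SD 5 |
|---|---|---|---|---|---|
| 5% | 0.8% | 1.9% | 3.1% | 3.7% | 4.2% |
| 10% | 1.6% | 3.8% | 6.3% | 7.4% | 8.4% |
| 25% | 4.0% | 9.4% | 15.7% | 18.6% | 21.1% |
| 50% | 8.0% | 18.8% | 31.4% | 37.1% | 42.1% |

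**Limit of the arithmetic.** It takes the window as the two adjacent calendar days. For daily activity the SAP also speaks of the two valid days before the bleed, which need not be adjacent when a day is not valid.

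**The case against.** The strongest reply is that the design is event-driven. Footnote 7 puts continuous reporting first, the schedule table says entry is made when bleeding occurs, and 6.4.1 gives the monthly step the role of confirmation. The EQ-5D-5L and pain VAS are also due at each bleeding episode. There are general safeguards: a treatment start date and time for treated bleeds, which is a second date anchor; investigator review of the plausibility of entries; retraining of patients; and a data review meeting before lock (SAP 3.4). The analysis is exploratory and descriptive.

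Most of this stands. The prompt is not shown to be a main route of entry. However, none of these safeguards is a rule on entry delay, and a plausibility review is unlikely to catch a date that is credible but one or two days off.

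A reader might infer two stronger things, and the documents support neither:

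- **That many pre-bleed days are wrong.** This depends on f and the error SD, and the documents give neither. Under the assumptions above, the share could be below 1%.
- **That date error could reverse the result.** Take an illustration with assumed inputs: activity at 1.30 times usual on the two true pre-bleed days, 0.5 times usual from onset to the third day after, and recall error uniform over −3 to +3 days. The mean ratio for recalled bleeds is (1 + 1 + 1.15 + 1.30 + 0.90 + 0.50 + 0.50)/7 = 6.35/7 = 0.907. Over all bleeds it is 1.30 − 0.393f: 1.26, 1.20 and 1.10 for f = 10%, 25% and 50%. It falls below 1 only if f exceeds 0.30/0.393, about 76%. The SAP also names no usual-activity comparator, so this ratio is not a planned output.

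**Conclusion.** The point holds in a limited form. The documents allow late entry with a recalled onset date, both pre-bleed analyses rest on a two-day window, and nothing in the SAP identifies or examines late-entered bleeds. That one day of error spoils half the window, and two or more days spoil all of it, follows from the window definition when the two days are adjacent calendar days.

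The overall effect is unknown: about 1% to 42% of window days wrong for f of 5% to 50% and an error SD of 0.5 to 5 days, with half of those days on or after onset if the error is symmetric. Downward bias further requires that activity falls after a bleed, which is plausible but not documented here. This is a cheap improvement to an exploratory analysis, and the case for it is that the lag can be measured from the study's own data.

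**What to change.** In SAP 4.4.2:

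1. For each bleed, derive the lag between ePRO entry date and recorded onset date, and tabulate it. This assumes that bleed entries carry a record date; the SAP already uses such dates to assign the EQ-5D-5L to months.
2. Add a sensitivity analysis, listed in 4.4.3, that repeats the summaries under *Bleeding and daily physical activity* and the prior-intensity split under *Treatment regimen for bleeding* for bleeds entered within a pre-specified short lag (for example 2 days), shown beside the all-bleeds results.
3. State that, if the two differ, the report will say that the all-bleeds result may be affected by date error.

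The cost is SAP wording, one derived variable and one extra column per table; data collection does not change. The restricted column will hold fewer bleeds, and promptly entered bleeds may differ from the others in severity, treatment or type of patient. It should therefore support the all-bleeds result and not replace it.
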